## **5.0 Treatments**

Study treatment is defined as any investigational treatment(s), marketed product(s), placebo, or medical device(s) intended to be administered to a study participant according to the study protocol.

Clinical supplies [study treatment(s) provided by the Sponsor] will be stored as a stock bottle at the Urology clinic in a locked area, accessible to only study staff. Supplies at the main facility will be obtained from the IDS pharmacy.

### **5.1 Treatments Administered**

5.1.1 The study treatment(s) to be used in this trial are outlined in section 4.2.

## **6.0 Dose Modifications**

Modifications to the dose will be made if Safety Concerns as outlined in 5.1.1 arise in the propranolol/surgery group.

### **6.1 Definition of a Safety Concern**

6.1.1 Safety Concerns in this study will include bradycardia or hypotension requiring intervention by the anesthesiologist beyond standard interventions to mitigate the condition (CTCAE grade 3 or greater), or any adverse event attributable to propranolol that results in a prolonged stay in post anesthesia care unit. If any event of this nature occurs during the study, the dose will be reduced as described in Section 5.2.1 for subsequent patients.

### **6.2 Dose Reduction**

6.2.1 If a subject has CTCAE grade 3 hypotension or bradycardia (as per section 5.1.1), the dose of propranolol will be reduced to 20 mg for subsequent patients. The study will be terminated if there is an additional CTCAE grade 3 event at the lowest dose of 20mg.

6.2.2 For any CTCAE grade 4 or 5 hypotension or bradycardia attributable to pre-operative propranolol dosing, the study will be terminated.

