#### **4.2 Methods**

#### **Compare activation of ADRB2/PKA/BAD signaling pathway in the prostate glands of men who take or do not take ADRB2-selective beta blockers**

##### **Patients scheduled for prostate biopsy.**

The research staff screens the OR and clinic schedules for potential patients and provides a list to the investigator. [name] or co-Investigator will discuss the study with the patient and inform the research nurse or coordinator (research staff) about the patients who agreed to participate in the study. Research staff will inform Tissue Procurement Lab (Director [name]; [name], Tumor Procurement Coordinator) and courier about the scheduled date and time when prostate samples will be collected.

On the day of sample collection [name] lab will prepare box with dry ice for prostate biopsy samples, a box with wet ice for blood samples as well as 2 ml cryovials (Corning, cat#430488) to collect biopsies and tubes to collect blood (Na heparin, green-capped tube, 10 ml total blood volume).

Courier will pick up boxes from Tissue Procurement Lab (Director [name]; [name], [contact]) and deliver to research staff at Charlois clinic ([name]).

Recruited patients scheduled for prostate biopsy will be randomized into two groups. Group one will receive 40 mg propranolol given by research nurse 2 hours prior to prostate biopsy. The research nurse should withhold drug and contact treating physician if SBP <120 or HR < 63. Group two will receive no treatment.

All patients will fill out stress surveys on the biopsy day.

All patients will give approximately 10 mL of blood approximately 20 min prior to prostate biopsy to test plasma catecholamine levels (collected in 10 mL green top tube (sodium heparin) and sent on ice within 1 hour to clinical lab for processing) and propranolol level (collected in 10 mL green top tube (sodium heparin) and sent on ice to The Tissue Procurement lab for processing and storage as described below). For group one that takes propranolol, this blood sample will be drawn at 1.5 -2 hours after taking the propranolol tablet.

For the biopsy, at least 1 core of the prostate specimen is to be flash frozen (on dry ice -80C) for laboratory analysis. Each biopsy sample will be collected into separate cryovials. The samples will be picked up by courier at Charlois clinic and delivered to Tissue Procurement laboratory.. The tissue samples will be frozen at -80 C.

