### **8.4 Interim Analysis**

An interim analysis will occur after 10 patients (5 in each group) are recruited to determine if dosing or administration route of propranolol needs to be adjusted. This interim analysis will not include any statistical testing, but rather will be used to assess the safety of the trial.

If CREB phosphorylation will be observed in patients with epinephrine blood levels over 1nM who took propranolol, the dose of propranolol will be increased to 80mg. Exclusion criteria for this dose will be reviewed based on interim analysis.

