### **Safety Review**

Safety will be addressed on a per patient basis as described in Section 5.0 and as reiterated below. Because this pilot study involves only 1 dose of medication (initially 40mg; if 40mg is not effective in inhibiting CREB phosphorylation dose will be increased to 80mg) with a peak effect expected in 1-4 hours and a half-life of 3-6 hours, the safety assessment window will be in the perioperative period for up to 4 hours after dosing. Blood pressure will be monitored at 3h and 4h after the propranolol is taken. Patients will be allowed to leave if SBP >90. If blood pressure not acceptable after 4 hours, the patient will continue to be monitored and may receive IV fluids if SBP/DBP <90/60 after 6h post dose.

If there is CTCAE grade 3 bradycardia or hypotension, then the dose for subsequent patients will be modified per section 5.2. The study will be terminated if grade 4 or 5 cardiac events attributable to propranolol dosing occur. While safety will be addressed promptly on a per patient basis, a review of all AEs will occur at the safety interim analysis after 10 patients have been accrued (5 in each group). If other safety events are identified by the investigators at this interval analysis, then the propranolol dosing may be modified for subsequent subjects as directed by Section 5.2 or in a manner designated by the PI to ensure safety of the patients.

Finally, if a safety event as described in Section 5.1.1 occurs, the study will be locked and all activities suspended for 24 hours to further evaluate patient recovery and to monitor for other potential events. If patient recovery is deemed acceptable by the PI, the trial will be unlocked with subsequent patients following the modified dose reduction plan as described in Section 5.2.

Occurrence of an SAE other than those listed above will be addressed following the SAE protocol (Appendix F).

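### Section 6.2.1 names 20 mg as the only dose after a grade 3 event, so an event after the conditional rise to 80 mg moves later propranolol patients to half of a dose the protocol has just described as not effective

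*Combined protocol and SAP*

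**What the plan says.** **Starting dose.** Section 4.2, for biopsy patients: "Group one will receive 40 mg propranolol given by research nurse 2 hours prior to prostate biopsy". The prostatectomy text gives the same dose.

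**Rise.** Section 8.4, Interim Analysis, sets the trigger: "If CREB phosphorylation will be observed in patients with epinephrine blood levels over 1nM who took propranolol", then "the dose of propranolol will be increased to 80mg". The Safety Review under 8.4 gives the reason: "if 40mg is not effective in inhibiting CREB phosphorylation dose will be increased to 80mg".

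**Reduction.** Section 6.2.1, after a grade 3 hypotension or bradycardia event: "the dose of propranolol will be reduced to 20 mg for subsequent patients". It then adds: "The study will be terminated if there is an additional CTCAE grade 3 event at the lowest dose of 20mg". No dose in use at the time of the event is named. The Safety Review, which itself mentions 80 mg, refers grade 3 bradycardia or hypotension to this same rule. It cites the rule as section 5.2; the text now stands at 6.2.

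**Adverse event review.** The Safety Review says that "a review of all AEs will occur at the safety interim analysis after 10 patients have been accrued (5 in each group").

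**Analysis.** Section 8.2 compares the two randomised groups on CREB phosphorylation with one two-sample t-test and gives descriptive statistics by group. It does not mention dose received.

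**The concern.** The dose can go up under 8.4 and down under 6.2.1, but the two rules do not refer to each other's levels. The reduction rule reads as if written for a 40 mg start, where 20 mg is the next level down. Once 80 mg is allowed, the same words produce a move past the starting dose to a level below the one whose apparent lack of effect prompted the rise. Nothing in the documents shows that this was intended.

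Two things are at stake. The first is conduct: later men would be randomised to a dose that, on the protocol's own description, is less likely to inhibit the primary marker than one already found wanting. The second is interpretation: the treated arm could contain men at 40, 80 and 20 mg, analysed as one group. A null result could then reflect the sequence of doses and not the drug, and the plan has no statement to guard against that reading.

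**Working it through.** The sample-size figure is not in dispute. With 25 evaluable men per group, a difference of 0.21, SD 0.26 and two-sided alpha 0.05 (section 8.1), the noncentral t distribution on 48 degrees of freedom gives 79.9% power, against the stated 80%. The point rests on following the dose rules in order.

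1. **Start.** 40 mg (section 4.2). The interim comes after 10 patients, 5 of them on propranolol (8.4).
2. **Rise, if triggered.** 40 mg to 80 mg (8.4). Section 3.0 plans 30 propranolol patients, so 30 − 5 = 25 of them come after the interim.
3. **Grade 3 event at 80 mg.** The Safety Review refers to the reduction rule, whose only destination is 20 mg (6.2.1). The cut is (80 − 20)/80 = 75%. The new dose relative to the starting dose is 20/40 = 50%.
4. **How many could be affected.** At least one man must have been dosed at 80 mg for the event to occur, so at most 25 − 1 = 24 of the planned 30 could be assigned to 20 mg by this route. Recruitment beyond 60, which section 3.0 allows if evaluable samples fall short, would raise that ceiling.
5. **Is there another route?** The Safety Review lets the principal investigator choose a different modification, but only for other safety events identified at the interim. It does not cover grade 3 bradycardia or hypotension at 80 mg after the interim. After the 24-hour lock, the same section again sends subsequent patients to the reduction rule. No section gives a step from 80 mg to any level other than 20 mg.
6. **Is the event review timed to cover 80 mg?** The rise is decided at the 10-patient interim, and the only scheduled review of all adverse events takes place at that interim. No one can have taken 80 mg by then. Section 8.4 says that the exclusion criteria will be reviewed for the higher dose, but it schedules no second all-event review.
7. **Analysis.** The possible treated arm is 40 mg (up to and including the interim), 80 mg (until the event) and 20 mg (after it). Section 8.2 gives one pooled comparison and no rule for different doses.

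**The case against.** **The rule is complete as written.** Section 6.2.1 names no starting dose, so an event at 80 mg does have a defined action: go to the lowest dose. Preferring an intermediate step would be a clinical judgement. This stands, and no step is preferred here. What remains is that the destination conflicts with the protocol's own reason for raising the dose, and the documents do not acknowledge it.

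**Not effective is a strong phrase for a weak observation.** The operative trigger is phosphorylation seen in treated men with epinephrine over 1 nM, among about 5 treated men, in a review without statistical testing. That is not a demonstrated null for 40 mg, still less for the difference in means between arms. This stands. A reader might infer that a trial continuing at 20 mg cannot answer its primary question; the documents do not support that.

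**Safety oversight continues at 80 mg.** A reader might infer that the highest dose gets the least safety review. Against that, propranolol use is monitored continuously (section 1.0). The 24-hour lock and the termination rule for grade 4 or 5 cardiac events attributable to propranolol are not limited by dose (8.4). All adverse events are entered in WISER, and the DSMC reviews reported serious events and can suspend the trial (Appendix F). Only the narrow statement survives: the scheduled all-event review precedes any 80 mg dosing.

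**A power loss cannot be charged to this gap.** A reader might model full effect at 80 mg and none at 40 or 20 mg. In that model, moving men to 20 mg or to 40 mg gives identical power, so the calculation measures leaving 80 mg at all. Nor is 80% the right comparator. If the first 5 treated men took 40 mg and are all evaluable, the shift is 0.21 × 20/25 = 0.168 and power is about 61% with no safety event. That loss, like the 40/80 mg mixture, comes from the rise itself. The documents give no dose-response, event rate or probability of escalation, so the likelihood of the full sequence cannot be stated either.

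**Conclusion.** The concern holds as an inconsistency between 6.2.1 and 8.4 that affects both conduct and interpretation. If the dose has been raised, one grade 3 hypotension or bradycardia event moves all later patients in the propranolol group from 80 mg to 20 mg, half of the dose the protocol has just described as not effective. At most 24 of the planned 30 propranolol patients could be assigned to 20 mg this way. The arm could then mix three doses in one pooled t-test.

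The conclusion rests on a literal reading of 6.2.1 and on two conditional steps: the rise is triggered, and a grade 3 event then occurs at 80 mg. It does not depend on any assumed effect or event rate, and it does not show a particular loss of power or a lack of safety oversight at 80 mg. The point is worth correcting because the change is cheap and the sequence is one the protocol itself permits.

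**What to change.** - **Sections 6.2.1 and 8.4.** The sponsor must reconcile them so that the action after a safety event is stated for each dose level the protocol allows (20, 40 and 80 mg), with the cross-references to 5.1.1, 5.2 and 5.2.1 corrected to the current numbering. No dose or clinical rule is proposed here.
- **Section 8.4.** State whether the review of all adverse events applies to the raised dose, given that the scheduled one precedes it.
- **Section 8.2.** Keep the pooled randomised comparison as the primary analysis. Add a descriptive report of CREB phosphorylation by dose received. State that, if men were moved to a dose at or below one judged not effective at the interim, a pooled null will not be read as lack of pathway inhibition by propranolol.

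The cost is protocol wording and a few descriptive tables, with no extra patients. The dose Surgery Day Worksheet (Appendix N) already records the dose given. The downside is that the dose subgroups will be small and were not formed by randomisation between doses, so they can only be described.

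### For attributable grade 4 or 5 hypotension or bradycardia, the safety rules order both dose reduction and termination, and no precedence is stated

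*Combined protocol and SAP*

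**What the plan says.** The rules stand in four places.

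- **Section 6.0** changes the dose if "Safety Concerns as outlined in 5.1.1 arise in the propranolol/surgery group". That group is not defined.
- **Section 6.1.1** gives two kinds of Safety Concern. The first is "bradycardia or hypotension requiring intervention by the anesthesiologist beyond standard interventions to mitigate the condition (CTCAE grade 3 or greater". The second is "any adverse event attributable to propranolol that results in a prolonged stay in post anesthesia care unit". One instruction follows for both: "If any event of this nature occurs during the study, the dose will be reduced as described in Section 5.2.1 for subsequent patients".
- **Section 6.2** has two parts. Under 6.2.1, a grade 3 hypotension or bradycardia event, qualified by a reference back to the definition, lowers the dose to 20 mg; a further grade 3 event at 20 mg ends the study. Section 6.2.2 reads: "For any CTCAE grade 4 or 5 hypotension or bradycardia attributable to pre-operative propranolol dosing, the study will be terminated".
- **The Safety Review under 8.4** modifies the dose after grade 3 bradycardia or hypotension and then states: "The study will be terminated if grade 4 or 5 cardiac events attributable to propranolol dosing occur". Its later paragraph on safety events suspends all activity for 24 hours. If the principal investigator finds the patient's recovery acceptable, "the trial will be unlocked with subsequent patients following the modified dose reduction plan".

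These rules cite Sections 5.1.1, 5.2 and 5.2.1. In the current numbering, 5.1.1 is a pointer to the treatment description, and 5.2 and 5.2.1 do not exist.

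**The concern.** These are the protocol's own event-triggered rules for a drug given about two hours before a procedure. Thirty men are planned to receive it, and 8.4 allows an increase to 80 mg. If a grade 4 hypotension occurs, staff need to know at once whether the trial is over or may reopen after the 24-hour lock. As written, each course can be defended by citing a mandatory sentence. At stake are the safety of the next patients and whether the trial continues at all. The sample-size calculation is not affected.

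**Working it through.** The plan gives no figure on this point, so the check is a comparison of the texts. The section numbers are read with the evident shift of one (5.1.1 as 6.1.1, 5.2 as 6.2). The Safety Review is split into its grade-based sentences and its lock paragraph.

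| Event | 6.1.1 | 6.2 | Safety Review, by grade | Safety Review, lock paragraph | Result |
|---|---|---|---|---|---|
| Grade 3 hypotension or bradycardia, prostatectomy, anesthesiologist intervenes | Reduce | Reduce (6.2.1) | Modify dose | Lock, then possible restart at reduced dose | Consistent |
| Grade 4, attributable, same setting | Reduce | Terminate (6.2.2) | Terminate | Lock, then possible restart at reduced dose | Conflict |
| Grade 5, attributable, same setting | Reduce | Terminate (6.2.2) | Terminate | Restart condition cannot sensibly be met | Conflict between 6.1.1 and the rest |
| Other attributable grade 4 or 5 cardiac event | Covered only if it prolongs the recovery-unit stay | 6.2.2 silent | Terminate | Applies only if 6.1.1 is met | Scope mismatch |
| Attributable event prolonging the recovery-unit stay, below grade 3 | Reduce | 6.2.1 gives the reduced dose but does not list this trigger | Silent | Lock, then possible restart at reduced dose | One instruction |
| Grade 3 hypotension or bradycardia, clinic biopsy patient | Unclear | Unclear (6.2.1 imports the definition) | Modify dose | Unclear | Coverage unclear |

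**Grades 4 and 5.** The words "requiring intervention by the anesthesiologist beyond standard interventions to mitigate the condition (CTCAE grade 3 or greater" bring grades 4 and 5 into 6.1.1, and its instruction covers every event so defined. Section 6.2.2 takes the same events, where attributable, and ends the study. The lock paragraph relies on the same definition and does not exclude grade 4. All these instructions are mandatory, and no sentence ranks them.

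**Attribution.** Section 6.2.2 requires attribution to propranolol. The hypotension and bradycardia part of 6.1.1 does not. A grade 4 event judged unrelated would therefore reduce the dose under 6.1.1, while 6.2.2 says nothing.

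**Events that terminate.** Section 6.2.2 names hypotension and bradycardia; the Safety Review says cardiac events. Section 13.1 lists congestive heart failure and intensified AV block under cardiovascular events. At grade 4 and attributable, these would plausibly end the study under the Safety Review but are outside 6.2.2.

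**Biopsy patients.** Both parts of 6.1.1 depend on an anesthesiologist or a recovery unit. In Section 4.2, the biopsy pathway runs at a clinic and names a research nurse and the treating physician; only the prostatectomy pathway names an anesthesiologist. The Safety Review acts on grade 3 alone. Whether a clinic event meets the definition is therefore unclear. This is an inference, because the protocol does not say that the clinic lacks these resources.

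**How often it could matter.** The documents give no event rate. For illustration, assume an independent per-patient risk p of an attributable grade 4 or 5 event among 30 treated men. The chance of at least one is 1 − (1 − p)^30:

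- p = 0.5%: 14%
- p = 1%: 26%
- p = 2%: 45%
- p = 5%: 79%

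These rates are assumed, and the point does not depend on them.

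**The case against.** The strongest reply is that the sections, read together, form one ladder: grade 3 reduces the dose, a further grade 3 at 20 mg terminates, and attributable grade 4 or 5 terminates. Section 6.1.1 sends reduction to what is now 6.2.1, which covers grade 3 only. The lock paragraph reopens the trial under what is now 6.2, which contains 6.2.2, and reopening is conditional, not automatic. This is a reasonable reading and may be the intended one. But the protocol states no such precedence, the definition includes higher grades in terms, and the lock paragraph makes no exception for them. A stopping rule should not rest on that inference.

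Other parts of the reply succeed. They answer stronger readings that a reader might infer:

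- **Every mismatch is a pair of opposite actions.** For cardiac events other than hypotension or bradycardia, 6.2.2 is silent and does not say to continue. The Safety Review presents itself as a restatement, so its wider term may be loose wording.
- **A prolonged recovery-unit stay without grade 3 leads to no action.** Section 6.1.1 orders reduction for it. Its absence from the trigger in 6.2.1 does not cancel that.
- **Biopsy patients are outside the rules.** The protocol uses surgery loosely for both procedures: the Surgery Day Worksheet serves both, and Appendix B has one propranolol arm covering both. Section 6.2.2 and the grade-based sentences of the Safety Review do not depend on the setting.
- **This is the only safety stop.** Appendix F lets the Data and Safety Monitoring Committee suspend the trial, and 8.4 adds a review of all adverse events after 10 patients.

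The shifted section numbers would on their own be clerical.

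**Conclusion.** Wrong as written, within limits. The conflict is firm for attributable grade 4 hypotension or bradycardia that meets 6.1.1: reduce and continue, lock with possible restart, and terminate are all prescribed. At grade 5 the conflict is between reduction in 6.1.1 and termination elsewhere. The set of terminating events and the coverage of grade 3 events in clinic biopsy patients are mismatches of scope; the second rests on inference about the clinic setting.

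A reader might conclude that the safety stop as a whole is indeterminate. The documents do not support that: grade 3 hypotension or bradycardia in prostatectomy patients gets the same answer throughout, and a prolonged recovery-unit stay has one instruction. The conclusion assumes only that the references to 5.1.1, 5.2 and 5.2.1 mean 6.1.1, 6.2 and 6.2.1. The case rests on the consequence of such an event, since its frequency is not given.

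**What to change.** Reconcile 6.0, 6.1.1, 6.2.1, 6.2.2 and the Safety Review under 8.4 into one event-by-action table. It should have:

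- one list of qualifying events, settling whether termination covers hypotension and bradycardia only or cardiac events more widely;
- one grade threshold and one attribution condition for each action;
- one population that expressly covers both biopsy and prostatectomy, with triggers that can be assessed in either setting;
- an explicit statement of which action takes precedence at grades 4 and 5, and whether the 24-hour lock and restart apply to them.

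The Safety Review should then refer to the table instead of restating the rules, and the references to 5.1.1, 5.2 and 5.2.1 should be corrected. Which action applies to each event is for the sponsor's clinicians to decide. The cost is one table and corrected references in one amendment, with no change to sample size or analysis.

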## **3.0 Study Population**

Patients recruited will be individuals scheduled for prostate biopsy or prostatectomy. For this study, 60 individuals will be recruited. Patients will be randomized to receive the treatment (or not) for a total of 30 patients receiving propranolol prior to biopsy or prostatectomy and 30 patients receiving no treatment. It is expected that approximately 10 (5 patients in each group) may have non-evaluable tumor tissue. In case the number of evaluable tumors will be less than 25 for each group, more patients will be recruited to accumulate 25 evaluable samples for each group.

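### An attributable grade 4 non-cardiac event such as bronchospasm can fall outside every mandatory lock, dose-reduction and termination rule, and in a narrow case outside DSMC notice too

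*Combined protocol and SAP*

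**What the plan says.** The protocol sets out four mandatory responses to a serious reaction.

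- **Termination.** Section 6.2.2: "For any CTCAE grade 4 or 5 hypotension or bradycardia attributable to pre-operative propranolol dosing, the study will be terminated." The Safety Review in Section 8.4 is somewhat wider: "The study will be terminated if grade 4 or 5 cardiac events attributable to propranolol dosing occur." Section 6.2.1 also ends the study after a further grade 3 event once the dose is down to 20 mg.
- **24-hour lock.** Safety Review: "if a safety event as described in Section 5.1.1 occurs, the study will be locked and all activities suspended for 24 hours." The number 5.1.1 is an old cross-reference to what is now 6.1.1.
- **Dose reduction.** Section 6.1.1 applies it to any Safety Concern. Section 6.2.1 spells it out for grade 3 hypotension or bradycardia. Section 6.0 words dose modification for the propranolol/surgery group.
- **DSMC notice.** Safety Review: "Occurrence of an SAE other than those listed above will be addressed following the SAE protocol (Appendix F)." Appendix F then requires notice of unexpected grade 4 events, unplanned inpatient stays longer than 24 hours at any grade, and deaths. It asks that grade 4 events of doubtful expectedness be reported as well.

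Section 6.1.1 describes a Safety Concern in two limbs. The first is "bradycardia or hypotension requiring intervention by the anesthesiologist beyond standard interventions to mitigate the condition (CTCAE grade 3 or greater)." The second is not limited to blood pressure or heart rate, but it depends on the recovery stay: "any adverse event attributable to propranolol that results in a prolonged stay in post anesthesia care unit."

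Section 13.1 lists bronchospasm under respiratory events and anaphylactic reactions under allergic events. For the whole trial, the Safety Review schedules one review of everything: "a review of all AEs will occur at the safety interim analysis after 10 patients have been accrued (5 in each group)."

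**The concern.** The automatic rules follow the blood-pressure and heart-rate effects of propranolol. They do not follow the other serious reactions that the protocol itself lists. A grade 3 hypotension that meets 6.1.1 locks the study and lowers the dose for later men. A more severe airway reaction attributed to the same research dose may require neither.

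The setting makes this more relevant. Under Section 4.2, biopsy men are dosed by a research nurse, and their samples are collected at a clinic. Evaluation by an anesthesiologist before the procedure is described only for prostatectomy. Both limbs of 6.1.1 are worded around anesthesia care, so a man biopsied in clinic may have no PACU stay to prolong.

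DSMC notice matters because it is the written route to a documented suspension decision. Under Appendix F the reporter records whether the protocol should be suspended after speaking with the DSMC clinician, and the committee may disagree with the investigator. Without notice, that step is not reached.

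**Working it through.** The plan gives no figure to reproduce here, so the check is a trace through the rules.

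**Test event.** A grade 4 bronchospasm attributed to propranolol, without qualifying hypotension or bradycardia, in a man on the 40 mg dose.

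**Rule by rule**

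1. Termination under 6.2.2 needs hypotension or bradycardia: not met.
2. Termination under the Safety Review needs a cardiac event. Section 13.1 classes bronchospasm as respiratory: not met.
3. Termination under 6.2.1 needs an additional grade 3 event at 20 mg. Its event type is not restated, but it is worded for grade 3 and applies only after a reduction: not met.
4. Lock and dose reduction need a 6.1.1 event. The first limb is not met. The second is met only if the PACU stay is prolonged.
5. DSMC notice under Appendix F needs an unexpected or doubtful grade 4 event, or an unplanned inpatient stay over 24 hours. If the event is clearly expected, only the admission route is left.

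**The clearly expected event, with the two remaining triggers crossed**

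| Prolonged PACU stay | Unplanned admission >24 h | Lock and dose reduction | Termination | DSMC notice |
|---|---|---|---|---|
| No | No | No | No | No |
| No | Yes | No | No | Yes |
| Yes | No | Yes | No | No |
| Yes | Yes | Yes | No | Yes |

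The first row is the gap. If expectedness is doubtful or absent, the last column becomes Yes in every row and the other columns do not change. The table lists written routes; the rows are not equally likely.

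**Exposure after the scheduled review.** Section 3.0 plans "for a total of 30 patients receiving propranolol prior to biopsy or prostatectomy." The review of all adverse events comes when 5 of these have been recruited: 30 − 5 = 25, and 25/30 = 83%. These 25 have no further scheduled review of all events. Under Section 8.4 the dose could by then be 80 mg.

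**Frequency.** The documents give no event rate. As an assumption only, let p be the chance per dosed man of any attributable grade 4 non-cardiac event, with men independent. The chance of at least one in 30 is 1 − (1 − p)^30:

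- p = 0.01%: 1 − 0.9999^30 = 0.3%
- p = 0.1%: 1 − 0.999^30 = 3.0%
- p = 1%: 1 − 0.99^30 = 26.0%

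The first-row event is a subset of these, so each figure is a ceiling under its assumed rate and not an estimate of the gap.

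**The case against.** The strongest reply is that the conditions stack up. To escape all four responses, the event must be attributable, grade 4, non-cardiac and clearly expected, with no qualifying hypotension or bradycardia, no prolonged PACU stay and no unplanned admission over 24 hours. Appendix F keeps the reporting window open for 30 days after dosing. This stands, and it is why the point is minor.

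Expectedness is also less settled than it looks. Section 13.1 lists terms without grades. Section 13.2 sends the reader for expectedness to a Section 7.1 that is now the primary outcome. Appendix F lets a grade 4 event count as unexpected given the patient's health. Staff may well report a life-threatening reaction to one tablet in an elective patient. That narrows the missing DSMC notice, but it does not supply a lock or a dose decision.

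The wording of 6.1.1 says what Safety Concerns will include, so the list is not strictly closed. Keying rules to hemodynamics fits the systolic-pressure and heart-rate limits for eligibility and dose holding. The DSMC threshold is an institutional procedure. All fair, but none makes an action mandatory for the test event.

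A reader might go further in three ways that the documents do not support.

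- *Severe airway or allergic reactions in general go unaddressed.* Most routes through the rules reach a lock or DSMC notice.
- *Anaphylaxis is an equally clean example.* With qualifying hypotension it is caught, and whether grade 4 anaphylaxis can occur without it depends on CTCAE definitions that the documents do not reproduce.
- *Oversight lapses after patient 10.* Section 1.0 promises continuous safety monitoring, the Safety Review calls for prompt handling per patient, Appendix F requires all events in WISER, and Section 13.4 requires prompt IRB reporting.

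**Conclusion.** The point holds as a minor gap in the mandatory written actions. An attributable grade 4 non-cardiac event such as bronchospasm triggers no lock, dose reduction or termination unless it prolongs a PACU stay. Where it is also clearly expected and involves no unplanned admission over 24 hours, it requires no DSMC notice either. The case should be rare. Its frequency cannot be derived from the documents, and the primary comparison is not affected.

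The conclusion rests on four readings: old references to 5.1.1 and 5.2 mean 6.1.1 and 6.2; the Section 13.1 list serves as the list of expected events; bronchospasm is not a cardiac event; and a clinic biopsy may involve no PACU stay. The last is an inference, since the documents do not say where biopsy men recover. Section 6.0's reference to the propranolol/surgery group adds to the doubt but could simply mean the propranolol arm.

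**What to change.** 1. Add to 6.1.1: *any CTCAE grade 4 or 5 adverse event attributable to propranolol, in any care setting (biopsy or surgery)*. The existing 24-hour lock then applies.
2. Require in Section 13.3 that the DSMC be notified of every such event, whether or not it is expected. The institutional procedure in Appendix F need not change.
3. State that for these added non-hemodynamic events, dosing stays on hold until the DSMC clinician has advised on suspension or dose. Without this sentence, adding the events to 6.1.1 would set off its automatic dose reduction, and a smaller dose is not obviously the right answer to an airway or allergic reaction.
4. Align 6.2.2 with the Safety Review by using its cardiac-events wording.

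With items 1 and 2, all four rows of the table reach both the lock and DSMC notice.

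The cost is protocol wording only, using a lock and a notification channel that already exist. The downside is a possible brief pause for a rare event, which could outlast 24 hours if the DSMC advice takes longer.
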